## 5.6 Research criteria

In order to gather preliminary information on the efficacy of the experimental treatment clinical and MRI parameters will be recorded throughout the study.

We will evaluate:

- the proportion of disability progression-free patients at week 96;
- the longitudinal changes from baseline to visit week 96 in T25FW, 9-HPT, SDMT

Disability in MS is commonly measured by the Expanded Disability Status Scale (EDSS). The EDSS is based on a standard neurological examination, incorporating seven functional systems (visual, pyramidal, cerebellar, brainstem, sensory, bowel and bladder and cerebral) rated and stored as functional system scores (FSS). Each FSS is an ordinal clinical rating scale ranging from 0 to 5 or 6. These ratings are then used in combination with ambulation capacity to determine the EDSS score that ranges from 0 (normal) to 10 (death due to MS).

Sustained disability progression is defined as an increase of  $\geq 0.5$  EDSS points in the last 12 months. This change has not to be attributable to another etiology (i.e. fever, concurrent illness, MS relapse or concomitant medication) and has to be confirmed at a regularly scheduled visit after at least 12 weeks after the initial disease progression.

Brain MRI parameters: MRI is a useful tool for monitoring MS lesions. Different MRI derived parameters are used to assess paraclinical evidence of drug efficacy.

The following MRI parameters will be evaluated to address the research objective:

- brain and spinal cord atrophy as defined by percentage in brain and spinal cord volume change from baseline to week 96;
- number of new T2 brain and number of spinal cord lesions and changes in T2 lesion volume at week 96;
- number of new T1 hypointense lesions and changes in T1 hypointense lesion volume between baseline and week 96;
- total Gd-enhancing lesions in the brain and spinal cord MRI between baseline and week 96;
- other MR parameters including thalamic, cortical, white matter and normal appearing brain tissue average magnetization transfer ratio (MTR) – ancillary sub-study-.

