### 8.3 Study Procedure and Study Flow-chart

#### 8.3.1 Enrolment phase

Is the process of informed consent signature (described in the ethical consideration chapter). Starting from the signature of the informed consent by the patient or patients' legal tutors, the subjects will be enrolled in the clinical trial. When the enrolment is confirmed the patient screening number will be assigned consecutively in increasing order starting with '001'. The list will be filed with the investigator's file. After the enrolment of a patient in the study, the investigator sends the enrolment module to the principle investigator by fax or email to clinical research monitor.

Those protocol phases are foreseen after signature of the informed consent:

- **Screening/baseline phase**, during which the conditions required by the clinical protocol for patients' inclusion/exclusion will be assessed (screened subject). The duration will be of three weeks (+/- 3 working days). At the end of the screening phase, the inclusion/exclusion criteria of the study will be evaluated (enclosed subject).
- **Pre-treatment phase**: carried from the end of the screening phase to the day before the start of treatment.
- **Treatment phase**: The intrathecally administration of hNPCs will be performed on day 0. Prophylactical treatment with Tacrolimus will be performed for 96 weeks starting from day -7 whereas oral corticosteroids will be administered for the first 4 weeks.
- **Follow-up phase**: 96 weeks after the experimental drug administration day 0.

At the end specify if the end of total follow-up or single patient follow-up.

At the end of the total follow-up, for all patients enrolled and treated in the study is planned a long term follow up, in accordance with the national applicable laws and the international guidelines.

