### 8.3.5 Follow-up Phase

The follow-up phase will have a duration of 96 weeks. However the patients we'll be followed for the further 6 years at least.

Patients will attend control visits weekly for the first 4 weeks after hNPCs administration and then at 8 and 12 weeks. Starting from 12 weeks visits will be performed every 12 weeks. The procedures of each visit are described in details in the flow chart.

During the follow-up phase patients will receive tacrolimus, acyclovir, co-trimoxazole and folates for the entire follow-up (till week 96) and oral prednisone for 4 weeks.

The patient will undergo:

- Neurological visit with EDSS at week 4, 12, and then every scheduled visit
- T25FW, 9-HPT, SDMT at week 24, 48, 72, 96
- Haematological visit at week 4, 12, and then every scheduled visit
- General physical examination at every scheduled visit
- Record of vital signs at every scheduled visit
- AEs, SAEs record- Relapse Assessment at every scheduled visit
- Concomitant medication revision at every scheduled visit
- **Haematological blood tests comprehensive of:**

Complete blood count, extensive clinical laboratory evaluations will be performed at week 4, 12, 24, 48 and 96

Complete blood tests and biochemistry, urinalysis evaluation will be performed at week 2, 8, 36, 60, 72 and 84

Complete blood count evaluation will be performed at week 16, 20, 30, 42, 54, 66, 78 and 90

- Infectivological screening: CMV-DNA, EBV-DNA, Galactomannan detection will be performed at week 4, 12, 24, 48 and 96
- Immunological analysis: will be performed at week 4, 12, 24, 48 and 96
- Whole blood levels of tacrolimus will be obtained as reported in the specific section, in order to maintain a target of 5-10 ng/ml.
- CSF examination will be performed at week 12. During this visit the patient will be admitted to the hospital in the morning and will be discharged the day after (24 hours of observation after procedure). Complete chemico-physical evaluation, oligoclonal bands detection, CSF Cell evaluation, virological screening, ddPCR assays.
- Electrocardiogram, Chest Xray will be performed at visit week 48 e 96 and abdominal ultrasound only at visit 96
- Brain and spinal cord MRI at week 12, 24, 48 and 96
- Neurophysiological assessment (OCT, VEP, SSEP, MEP) will be performed at week 24, 48 and 96
- Administration of MsQuol54 will be performed at 12, 24, 48, 72 and 96 weeks

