**END OF STUDY VISIT:**

This visit will be performed 8 week after the end of treatment visit.

The patient will undergo:

- Neurological visit with EDSS
- Haematological visit
- General physical examination
- Record of vital signs
- AEs, SAEs record- Relapse Assessment
- Concomitant medication revision
- Haematological blood tests\_comprehensive of: Complete blood tests and biochemistry, urinalysis evaluation
- Infectivological screening: CMV-DNA, EBV-DNA, Galactomannan detection
- Administration of MsQuol54

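### EDSS worsening first seen at week 96 cannot be confirmed under the 12-week rule at any EDSS the protocol schedules, so the week-96 progression-free proportion can be slightly too favourable

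*Combined protocol and SAP*

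**What the plan says.** Section 5.6 lists among the research evaluations "the proportion of disability progression-free patients at week 96". The same section gives one definition: "Sustained disability progression is defined as an increase of" at least 0.5 EDSS points in the last 12 months, not explained by another cause, and the change "has to be confirmed at a regularly scheduled visit after at least 12 weeks after the initial disease progression".

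Section 8.3.5 sets the schedule. On visits: "Starting from 12 weeks visits will be performed every 12 weeks". On the EDSS: "Neurological visit with EDSS at week 4, 12, and then every scheduled visit". One further visit with an EDSS follows, the End of Study Visit: "This visit will be performed 8 week after the end of treatment visit". The end-of-treatment visit is not defined. Section 8.3.1 supports reading it as about week 96: "Prophylactical treatment with Tacrolimus will be performed for 96 weeks starting from day -7".

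Section 8.3.5 also promises longer observation, "However the patients we'll be followed for the further 6 years at least", and Section 8.3.1 mentions a long-term follow-up after total follow-up. Neither gives visit dates or an EDSS.

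Section 11 plans descriptive statistics and leaves the detail to an SAP still to be written. No section says how an unconfirmed worsening is classified.

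**The concern.** The endpoint is labelled week 96, but its definition needs a second rating at least 12 weeks after the first. Worsening that first appears at the week-96 visit would need a scheduled EDSS at week 108 or later, and none is scheduled.

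If the definition is applied as written, that patient has no confirmed progression and falls into the progression-free group. The error then runs one way, towards a more favourable result. Inclusion criterion 4 selects patients whose EDSS rose by at least 0.5 points in the previous 12 months, so further worsening late in follow-up is plausible. The trial is open label and the handling rule is unwritten, so the rule should be fixed before anyone sees which patients it affects.

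**Working it through.** The plan states no expected proportion, event count or power for this endpoint, so there is no figure to reproduce. The check is schedule arithmetic followed by a bound on the effect.

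**Step 1: which onsets can be confirmed.** Scheduled EDSS ratings (8.3.5): weeks 4, 12, 24, 36, 48, 60, 72, 84 and 96. The End of Study Visit is at 96 + 8 = week 104, reading end of treatment as week 96 and treating this visit as regularly scheduled.

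| Worsening first rated at | First scheduled EDSS at least 12 weeks later |
|---|---|
| Week 4 or 12 | Week 24 |
| Weeks 24, 36, 48, 60, 72 | The next 12-weekly visit |
| Week 84 | Week 96 (84 + 12), with week 104 as back-up (20 weeks) |
| Unscheduled visit, week 85 to 92 | Week 104 (92 + 12 = 104) |
| Week 96 | None: 104 − 96 = 8 weeks; week 108 needed, 4 weeks short |

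If end of treatment falls before week 96, the last rating moves earlier and the gap widens. No passage extends treatment beyond week 96.

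**Step 2: weight of one patient.** The maximum is 24 patients (8.1). With three in each of four cohorts (7.10) it is 12. One reclassified patient moves the proportion by 100/24 = 4.2 points or 100/12 = 8.3 points.

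**Step 3: upper bound under assumed rates.** The documents give no progression rate. Assume a constant annual risk r, every onset first detected at a 12-weekly visit, and every worsening truly sustained. With S(t) = (1 − r)^(t/52.18), t in weeks, the unconfirmable share is S(84) − S(96).

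| Assumed r | Progressed by week 96 | Confirmable (onset by week 84) | Difference | Share of week-96 progressors | Patients of 24 |
|---|---|---|---|---|---|
| 20% | 34% | 30% | 3.5 points | 10.4% | 0.8 |
| 30% | 48% | 44% | 4.4 points | 9.2% | 1.1 |
| 40% | 61% | 56% | 4.9 points | 8.0% | 1.2 |

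The last column is 24 times the unrounded difference. Setting the 96-week risk itself at 20% to 60% gives 2.3 to 4.9 points, or 0.5 to 1.2 patients of 24.

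**The case against.** Several stronger readings are tempting, and the documents do not support them.

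- A reader might infer that week-96 worsening can never be confirmed. At least six further years of follow-up are planned, so a later EDSS is possible. What stands is that none is dated or specified, while Section 5.6 asks for a regularly scheduled visit.
- A reader might infer that the plan classes these patients as progression-free. No passage says so, and the endpoint's own wording does not include sustained or confirmed. The SAP could censor them, list them separately or treat them as not evaluable. What stands is that the only written definition, taken literally, gives that result, and no alternative is written.
- A reader might infer that the last 12 of 96 weeks cannot yield an event. The rule ties only the confirmation to a regular visit. Section 8.3.5 plans unscheduled visits for new or worsening symptoms, with a neurological examination at the investigator's discretion, and onset rated there up to about week 92 could be confirmed at about week 104. Likewise, a short interval between weeks 84 and 96 does not lose a week-84 onset.
- Week 104 rests on reading an undefined term as week 96. That is fair, though an earlier date only widens the gap. The assessment table is only partly legible in the public text, so its EDSS row should be checked.

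Materiality is also limited. The endpoint is descriptive, in an uncontrolled phase I trial. At a proportion of 50%, the approximate 95% half-width is 1.96 × √(0.25/24) = 20 points with 24 patients and 1.96 × √(0.25/12) = 28 points with 12. The possible bias is well inside that. It is nonetheless directional and avoidable.

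**Conclusion.** The mismatch is real and confined to the last rating interval. The result rests on three readings: end of treatment means week 96 or earlier, the End of Study Visit is the last scheduled EDSS, and the 12-week rule is applied as written.

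The 3.5 to 4.9 points are a ceiling, not an estimate. The annual rates are assumptions, some week-96 worsening would not have been sustained, and some late onsets could be caught at unscheduled visits. In patients, this is about one of 24. The feasibility, safety and tolerability objective and the dose-escalation rules are unaffected. The point deserves a wording change before analysis and does not call for redesign.

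**What to change.** In Section 5.6 and the SAP, define the endpoint as free of progression with onset at or before week 84, confirmed at a scheduled EDSS at least 12 weeks later: week 96, or the End of Study Visit as back-up. List worsening first seen after week 84 without confirmation separately as unconfirmed, and add a sensitivity count that treats it as progression. State which week the end-of-treatment visit is. The cost is wording and a stated horizon 12 weeks shorter (12/96 = 12.5%).

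If the week-96 label is kept, schedule an EDSS at week 108 or later within the long-term follow-up already planned and name it as the confirmatory rating. For the last patient, week 108 falls 12 weeks (about 2.8 months) after week 96, just ahead of the draft statistical report that Section 8.2 places 3 to 4 months after the end of total follow-up. There is no need to move the End of Study Visit, which also carries infection screening, blood tests and adverse event review.

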## 6 Study Enrolment and Withdrawal

### 6.1 Inclusion criteria

1. Signature of the informed consent by the patient or patients' legal tutors
2. Age 18 to 55 years
3. Diagnosis of
  - a. Progressive MS as per the revised MC Donald 2010 criteria with a progressive course according to 2013 Lublin phenotypes classification (PMS) with failure or intolerance to all approved therapies according to the disease course or without any alternative approved therapy
4. Evidence of progression of disease defined by an increase of  $\geq 0.5$  EDSS points in the last 12 months
5. Disease duration 2 to 20 years (included)
6. EDSS  $\geq 6.5$
7. Presence of oligoclonal band in the CSF is required for Primary Progressive MS

### 6.2 Exclusion criteria

They will be excluded from the study patients:

1. with any active or chronic infection or diseases other than MS including but not limited to infection with HIV1-2, Hepatitis B or Hepatitis C and tuberculosis or immune deficiency syndromes;
2. treated with any immunosuppressive therapy, including but not limited to natalizumab and fingolimod, within the 3 months prior to screening;
3. treated with interferon-beta or glatiramer acetate within the 30 days prior to screening;
4. treated with corticosteroids within the 30 days prior to screening;
5. if relapse occurred during the 30 days prior to screening;
6. with contraindications for or intolerance to any medication, treatments and procedures that will be used in the study;
7. pregnant or in lactation or of childbearing age who are not willing to use a contraceptive method effective\* for the entire duration of the study;
8. who, in the opinion of the investigator, showing any condition that would preclude study participation.

\* refer to guideline [http://www.hma.eu/fileadmin/dateien/Human\\_Medicines/01\\_About\\_HMA/Working\\_Groups/CTFG/2014\\_09\\_HMA\\_CTFG\\_Contraception.pdf](http://www.hma.eu/fileadmin/dateien/Human_Medicines/01_About_HMA/Working_Groups/CTFG/2014_09_HMA_CTFG_Contraception.pdf)

### 6.3 End of Study Phase

*For single subject: regular termination.*

The participation of the patient in the study is regularly terminated:

- ظ End of the follow-up.
- ظ In case of death

*For single subject: premature termination.*

The patient may drop out of the clinical study at any time without stating reasons. This may not have any negative consequences for the patient's further treatment.

Possible reasons for withdrawal of the patient are:

- ظ Withdrawal of the consent.
- ظ Any clinical condition that in the Investigator's opinion could become dangerous for the patient and prevent the good conduction of the clinical trial.
- ظ Protocol violation that could compromise the quality of study data.

- ظ Lack of co-operation/compliance of the patient.
- ظ Occurrence of new diseases that could influence the treatment efficacy, for which the study medication is contraindicated or that are treated with a medication that is not permitted as a concomitant medication.
- ظ Lack of experimental treatment administration due to failure to release the Medicinal Product lot.
- ظ Lost to the follow-up.

The patients may withdraw from the study, if they decide to do so, at any time and for any reason. Patients who have been withdrawn from the study cannot be re-included in the trial.

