#### c) LONG TERM (day 15 - week 96)

- overall survival
- overall safety and tolerability measured by AE recording
- long term incidence of malignancies
- percentage of subjects with treatment-related mortality defined as death due to procedure and not to the course of disease
- evaluation of changes in quality of life measures
- changes in neurological conditions

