#### 6.3.1.2 Premature Termination or Suspension of study

This study may be temporarily suspended or prematurely terminated if there is sufficient reasonable cause or if any of the stopping criteria described in this protocol occurs. Circumstances that may warrant termination or suspension include, but are not limited to:

- determination of unexpected, significant, or unacceptable risk to participants;
- demonstration of efficacy that would warrant stopping;
- insufficient compliance to protocol requirements;
- data that are not sufficiently complete and/or evaluable;
- determination of futility;
- reconsideration of the risk/benefit ratio.

Written notification, documenting the reason for study suspension or termination, will be provided by the suspending or terminating party to <investigator, funding agency, the sponsor and regulatory authorities>.

If the study is prematurely terminated or suspended, the PI will promptly inform the Institutional Review Boards (IRBs) and/or Independent Ethics Committees (IECs), will provide the reason(s) for the termination or suspension and will instruct additional procedures to be followed in order to ensure that adequate consideration is given to the protection of the patient's interests.

For patients who have received the ATIMP, a long term safety follow-up it is required by law. Study may resume once concerns about safety, protocol compliance, data quality are addressed and satisfy the sponsor, IRB and/or CA.

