### **7.12 Prohibited Concomitant Therapy**

Concomitant treatment with any of the following is *not* allowed while receiving study treatment, unless as otherwise described in this protocol:

- Any non-study drug treatments directed toward the treatment of MS such as immunomodulatory treatments or chronic immunosuppressant therapy except tacrolimus
- Any investigational product, including investigational symptomatic therapies for MS and investigational therapies for non-MS indications

-Systemic steroid therapy including, but not limited to, oral corticosteroids (e.g., prednisone) or periodic (e.g., monthly) treatment with IV methylprednisolone, except for protocol-defined treatment of relapses as described above and course of oral prednisolone at the above mentioned dosage in the first 25 days after hNPCs injection.

Subjects who receive any of these restricted treatments may be required to permanently discontinue study treatment.

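### Section 6.3 lets a patient who already has the cells leave the planned visits to week 96, for example for a new disease or poor compliance, and later follow-up for the primary long-term endpoints is not secured

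*Combined protocol and SAP*

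**What the plan says.** Each patient receives one dose of cells on day 0 (sections 7.1 and 8.3.4). Section 5.3 c) sets primary endpoints that run from day 15 to week 96: survival, adverse events, "long term incidence of malignancies", "percentage of subjects with treatment-related mortality defined as death due to procedure and not to the course of disease", quality of life and neurological change.

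Section 6.3 gives possible reasons for taking a patient out of the study. They include a condition the investigator considers dangerous, a protocol violation that harms data quality, "Lack of co-operation/compliance of the patient", and "Occurrence of new diseases that could influence the treatment efficacy, for which the study medication is contraindicated". The new-disease entry continues with "or that are treated with a medication that is not permitted as a concomitant medication". One entry, failure to release the product lot, can only arise before injection. The others are not tied to a time. The section adds: "Patients who have been withdrawn from the study cannot be re-included in the trial". Death is listed as a regular end of participation, not as a withdrawal.

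For withdrawn patients, section 6.3.1 asks for an assessment on the end-of-study-visit model, where possible. Section 7.12 covers prohibited drugs: "Subjects who receive any of these restricted treatments may be required to permanently discontinue study treatment".

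Other places bear on follow-up after dosing. Section 6.3.1.2, on stopping the whole study, states: "For patients who have received the ATIMP, a long term safety follow-up it is required by law". Section 8.3.1 plans long-term follow-up for everyone enrolled and treated, beginning when total follow-up ends. Section 8.3.5 mentions at least six further years. Section 11 plans descriptive statistics and leaves detail to a later SAP.

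**The concern.** Once the cells are in, exposure cannot be stopped. Leaving the study after day 0 therefore ends observation but not exposure. Section 6.3 does not make that distinction, so a site can read it as permission to end a dosed patient's visits for a reason that is itself a health outcome (a new disease, a dangerous condition) or may follow from one (poor compliance).

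Loss of that kind may be informative: those who leave may differ in later risk from those who stay. The endpoints affected are primary. The protocol itself treats tumour formation as a risk (section 3.6.2.2) and reports two late-onset graft-derived tumours in other cell studies (section 5.5.1), so late observation matters here.

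**Working it through.** **1. What a withdrawn, dosed patient stops receiving.** Under section 8.3.5, post-dose brain and spinal MRI is planned at weeks 12, 24, 48 and 96, chest X-ray at weeks 48 and 96, and abdominal ultrasound at week 96 only. The end-of-study visit in the same section lists neurological, haematological and physical examinations, vital signs, adverse events, relapse assessment, concomitant medication, blood and urine tests, viral and fungal screening, and the quality-of-life questionnaire. It lists no MRI, X-ray or ultrasound. A patient withdrawn at, say, week 40 would have had two planned post-dose MRIs and no planned post-dose X-ray or ultrasound.

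**2. What is still captured.** All adverse events go on the CRF (section 5.5.7). Events are followed to resolution or stabilisation, and for serious ones this may continue after the patient leaves (section 5.5.8). A serious event that causes dropout goes through pharmacovigilance (section 6.3.1).

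**3. What is not secured.** For a patient withdrawn by the investigator, no section requires a search for a new, later event up to week 96. Section 6.3.1 seeks health status only for patients lost to follow-up. The follow-up in sections 6.3.1.2, 8.3.1 and 8.3.5 does not name individually withdrawn patients, does not restore missed visits, and is not linked to the week-96 endpoints.

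**4. Sample size.** The plan's maximum reproduces: 4 cohorts × 6 = 24. If all four cohorts are filled without expansion, the minimum is 4 × 3 = 12. The protocol states no event rate, dropout rate or precision target.

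**5. Illustration of size.** Assumptions: *w* dosed patients are withdrawn, no event is seen, and withdrawn patients leave the denominator. The exact one-sided 95% upper bound is 1 − 0.05^(1/n), with n = N − w.

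| Withdrawn (assumed) | N = 12 | N = 24 |
|---|---|---|
| 0 | 22.1% | 11.7% |
| 1 | 23.8% | 12.2% |
| 2 | 25.9% | 12.7% |
| 3 | 28.3% | 13.3% |
| 4 | 31.2% | 13.9% |
| 6 | 39.3% | 15.3% |

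For example, 1 − 0.05^(1/12) = 0.221 and 1 − 0.05^(1/9) = 0.283. The table treats a withdrawn patient as contributing nothing, so it shows the most precision that could be lost.

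**6. Bias.** One missed event moves the proportion by 1/12 = 8.3 points or 1/24 = 4.2 points. In the worst case for three withdrawals, where each had a later unseen event, the true proportion would be 3/12 = 25% (exact two-sided 95% interval 5.5% to 57.2%) or 3/24 = 12.5% (2.7% to 32.4%), against a reported zero. Leaving withdrawn patients in the denominator as event-free keeps the 22.1% or 11.7% bound but does not remove this bias. Only ascertainment does.

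**The case against.** A reader might infer that the week-96 endpoints lose the patients most likely to have had an event. The documents do not support that. If a tumour or a serious infection leads to withdrawal, the event comes first, so it is already recorded and, if serious, followed. A death on study is counted. Only a second or later event, or the remaining scheduled assessments, can be lost.

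A reader might also infer that taking any prohibited drug, including another MS treatment, is a listed ground for leaving the study, and that 7.12 then contradicts 6.3. This goes too far. In 6.3 the non-permitted drug appears only as treatment of a new disease. Section 7.11 allows medication needed to treat adverse events, and section 5.5.2 describes managing infections without mentioning study exit. Both 6.3 and 7.12 are permissive, so no withdrawal is mandated. What remains is that 7.12 does not say what study treatment means once the single dose has been given.

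The best defence of the plan is its long-term follow-up of treated patients. Survival and malignancy are cumulative and can be ascertained without every visit, and the SAP may yet set the denominator and censoring. That defence softens the point. It does not help quality of life or neurological change at week 96, and it leaves unsaid whether a patient withdrawn individually is included. Dose escalation rests on dose-limiting toxicities with a wait of at least three months (section 7.10), and no effect on it has been shown.

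**Conclusion.** The point holds as a gap in securing follow-up, and it should be fixed. A dosed patient can be withdrawn with no assured observation to week 96, and the reasons allowed make informative loss possible. No planned analysis has been shown to be biased. The figures rest on an assumed number of withdrawals and, for the bounds, on a completers-only denominator that the protocol does not state. On those assumptions the loss of precision is modest at 24 patients (11.7% to 13.3% with three withdrawn) and larger at 12 (22.1% to 28.3%). The possible bias from unseen later events matters more than the wider bound.

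**What to change.** In 6.3 and 6.3.1, separate stopping study medication or procedures from leaving follow-up. Leave the investigator's safety-based decisions on treatment unchanged, and keep death as regular termination.

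For dosed patients, record the listed reason and its date on the CRF, then continue the planned visits to week 96 as far as consent and the patient's condition allow. Where visits cannot continue, ascertain at least vital status and malignancy.

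Reconcile 6.3 with 7.12 by stating what study treatment means after day 0. State in 6.3.1.2, 8.3.1 and 8.3.5 that follow-up of treated patients includes those withdrawn individually.

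In the SAP, use all dosed patients as the safety denominator, state the censoring rule, and add a worst-case sensitivity analysis for withdrawn patients with incomplete follow-up.

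The cost is protocol and SAP wording and a CRF field for the reason and date; the visits are already planned. The small downside is that some data will come from patients on other drugs and must be flagged.
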